#### 4.5.10 Visus determination in Mydriasis using Autorefractometers:

For all three autorefractometers, following the standard miosis measurement, it is tested whether reliable refraction readings can be obtained for the far and near parts of the IOL by focusing on the lense's upper and lower halves of the dilated pupil.

20 to 30 minutes after drug dilatation of the pupils (depending on the reaction of the patient's eye), the procedures listed under 4.5.4.a, b and c are repeated. By contrast, this measurement should initially focus on the upper half of the lens, as far as possible. When the device has triggered and the measured values have been

collected, the data is transferred to the electronic patient record in FIDUS and saved. Subsequently, the process for the lower part of the lens is repeated.

If values scatter too high in 5 to 10 measurements this test procedure is completely stopped and carried on with point 4.5.6.

Pupil width in mydriasis is carried out with the Auto Kerato Refractometer KR-800s (TOPCON, Willich, Germany). This is achieved by pressing the "corneal diameter" button (description under 4.5.4.b). A measurement window with two positioning bars appears. Moving the bars to the right and left of the eye using the displayed control keys will display the width of the pupil.

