#### 4.5.11 Determination of the focal point in the far and near part of the intraocular lens in Mydriasis using the eye refractometer PR60 or PR50 (Rodenstock, Munich)

(Location: PR50 Cataract center, room B.5.50, Ambulance, room B.6.31+32  
PR60 Ambulance, room B.6.35)

The doctor ensures that the scale of the observer eyepiece is set to 0, or that his own ametropia is correctly taken into account. It is important that the patient's pupils are sufficiently dilated, since the visible annular illumination zone must be placed completely or at least for the most part in the patient's pupil plane. The doctor looks at the test mark images on the retina on the observation beam path and focuses them. The measured value is then read from a scale in diopters. This measuring process is carried out for the far part as well as for the near part of the IOL. For this purpose, the investigator tries to irradiate most of the annular illumination beam path through the far or near part of the IOL.

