#### 4.5.12 Determination of the focal point in the far and near part of the intraocular lens in Mydriasis using the iTrace (TraceyTechnologies, Houston, Texas, USA)

(Location: functional diagnostics)

The room lighting is darkened and the window blinds closed. The patient is positioned with the chin on the chin and forehead on the appropriate rests. Afterwards, the patient's head is turned slightly sideways so that the iTrace measuring head can be moved towards the patient's eye. The patient is asked to look through the iTrace and focus on a distant object. It is important to ensure that nothing blocks the patient's gaze, as this affects the patient's accommodation and may result in unwanted refractive readings.

The following measurements are taken in manual mode by selecting the single red wavefront icon in the upper right corner of the screen. The white target is first positioned on the edge of the entrance pupil, outside the center. At the same time, the iTrace is moved back and forth to focus on the iris details and thus set the most suitable measurement plane. The patient is asked to focus on the red light. Pressing the Enter key makes the red scan points visible. For the following measurements the separate 1 mm scan button (64 points) is selected. The scan pattern is centered on the optic center of the implanted multifocal lens. It is important to ensure that the scan pattern is located exactly between the two lens markings of the optics. The patient is asked not to move, to blink twice and then open both eyes wide. The fixation light is switched off with F10. Pressing the button on the joystick triggers the measuring process. If the wavefront measurement points are validly evaluable (visible within the pupil), the measurement is confirmed and saved by selecting the green check mark symbol. Otherwise, the measurement is repeated until a valid evaluation is possible.

Subsequently, a decentered measurement is carried out, 1.5 mm away from the optical center of the multifocal lens in the IOL far and near part, respectively. It is decentered at right angles to the apparent IOL markers and the 1 mm scan pattern is moved from the IOL center 1.5 mm (estimated based on the presented

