#### 4.5.14 Slit lamp microscopy in Mydriasis (Location: Ambulance, room B.6.31, B.6.32, B.6.35)

The investigator carries out the ophthalmological examination via a microscope. It is used to observe the eye under high magnification to assess the anterior, middle and posterior structures of the eye and to document any abnormalities or anomalies.

After disinfection of the chin and forehead rest, the patient places his head in the appropriate device. With the aid of various enlargements, the examining doctor has the opportunity to observe the anterior section of the eye in diffuse light first. These include the eyelids, the cornea, the conjunctiva, the anterior chamber, the iris and the pupil. The light is then limited to a slit of about 0.5 mm. This is done by a controller that can individually set the slit size. Now, the front structures are shown by pivoting the slit from different sides in different light incidence angles of the slit light in section.

Subsequently, the assessment of the multifocal intraocular lens is performed. The investigator examines the IOL through the slit for translucency, both in progressive and in regressive light, assesses the anterior capsule and determines

the diameter of the rhexis. Furthermore, it is checked whether the lens sits in the middle of the rhexis or whether it may have come to a decentration. By rotating the slit, the axis position of the multifocal IOL can now be examined. The narrow slit is turned so that it runs parallel to the visible axis of the IOL. Then the investigator can read the axis position on the slit lamp according to the TABO scheme.

For the assessment of the posterior structures of the eye – vitreous, optic nerve and retina or macula – the investigator additionally requires a 90-dpt magnifying glass. The investigator manually places the magnifying glass about 3 cm in front of the patient's eye with progressive light.

Finally, after completion of all examinations, the examiner documents the findings in the data collection sheet as well as the electronic patient file in FIDUS.

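### The autorefractors are aimed at the upper and lower halves, but the PR50/PR60 and iTrace at the lens's own far and near parts, so autorefractor far and near readings may mix both parts in markedly rotated lenses

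*Protocol*

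**What the plan says.** Section 4.5.10 repeats the autorefractor readings after dilation. Its purpose is stated as a test: "it is tested whether reliable refraction readings can be obtained for the far and near parts of the IOL". The means is "focusing on the lense's upper and lower halves of the dilated pupil", and the working instruction is "this measurement should initially focus on the upper half of the lens, as far as possible", followed by the lower part. No lens mark, lens axis or minimum pupil is named. One safeguard is given, without a numerical limit: "If values scatter too high in 5 to 10 measurements this test procedure is completely stopped".

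The other two mydriatic methods are referred to the lens itself:
- **PR50/PR60 (4.5.11):** "the investigator tries to irradiate most of the annular illumination beam path through the far or near part of the IOL".
- **iTrace (4.5.12):** the pattern is first centred between the two lens marks. For the far and near readings, "It is decentered at right angles to the apparent IOL markers and the 1 mm scan pattern is moved from the IOL center 1.5 mm". The whole 1 mm pattern must lie inside the pupil.

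The lens axis is read in section 4.5.14, the last examination listed: "By rotating the slit, the axis position of the multifocal IOL can now be examined". Section 4.4 lists the axis (TABO scheme) and the mydriatic pupil width among the data collected. Nothing feeds the axis back into 4.5.10.

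**The concern.** Section 2.1 sets out to find an accurate objective method, and section 5 asks which method is accurate and reproducible against subjective refraction. That comparison needs far and near to mean the same lens region for every device. Upper and lower halves coincide with the far and near parts only when the line between the parts lies horizontally. If the lens is rotated, an autorefractor aimed straight up or down can straddle that line, while the iTrace, which follows the marks, stays inside one part.

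Part of the autorefractor's disagreement with the reference could then come from where it was pointed and not from how well it measures. The iTrace is the device whose suitability the Background sets out to test, and an error of this kind would count only against its comparators. Because this is a measurement instruction, analysis can stratify or flag affected eyes afterwards but cannot separate a mixed reading into its two parts.

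**Working it through.** The protocol has no figure of its own to reproduce here. The check is geometric.

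**Inputs from the protocol**
- Optic 6 mm across, half far and half near (Background).
- iTrace pattern 1 mm, moved 1.5 mm from the lens centre at right angles to the marks (4.5.12).

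**Assumptions**
- Autorefractor zone: a circle of diameter d = 2, 2.5 or 3 mm. The protocol gives no value.
- Autorefractor offset: c = 1.5 mm straight up or down, borrowed from the iTrace. Section 4.5.10 gives no offset.
- Rotation θ: 20 to 60 degrees. The protocol gives no distribution.
- The pupil is wide enough for the zone at that offset.

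**Formulas**

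With the zone centred vertically, its distance from the far/near border is h = c·cos θ. With r = d/2 and u = h/r, the share of the zone in the wrong part is the circular segment

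f = [arccos(u) − u·√(1 − u²)] / π for u < 1, and 0 for u ≥ 1.

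Mixing starts where cos θ = r/c.

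**Worked case: d = 3 mm, θ = 45°**

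r = 1.5, h = 1.5 × 0.7071 = 1.061, u = 0.7071.
f = (0.7854 − 0.5000) / 3.1416 = 0.091, or 9.1%.

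**Results: share of the zone in the wrong part**

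| Assumed zone | Mixing starts at | 20° | 30° | 45° | 60° |
|---|---|---|---|---|---|
| 3 mm | any rotation above 0° | 0.9% | 2.9% | 9.1% | 19.6% |
| 2.5 mm | about 34° | 0% | 0% | 3.5% | 14.2% |
| 2 mm | about 48° | 0% | 0% | 0% | 7.2% |

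**Same offset, aimed by the marks**

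Now h = 1.5 mm whatever the rotation. For the iTrace, r = 0.5 mm, so u = 3 and f = 0. For an autorefractor zone of up to 3 mm, r ≤ 1.5 mm, so u ≥ 1 and again f = 0. Every share in the table therefore comes from the aiming rule and would vanish with lens-referenced aiming.

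**In dioptres, for scale only**

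Assume a far-near difference of 2 to 3 D and simple area weighting; the protocol gives neither. At 45° the shift is then 0.091 × 2 = 0.18 D to 0.091 × 3 = 0.27 D for a 3 mm zone, and 0 for a 2 mm zone. At 60° it is 0.39 to 0.59 D for 3 mm (0.196 × 2 and × 3), and 0.14 to 0.22 D for 2 mm (0.072 × 2 and × 3).

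**The case against.** **The step is exploratory and can be stopped.** Section 4.5.10 tests feasibility and ends if values scatter too much. This limits what is at stake. It does not remove the point: the test is fair only if the device is aimed at the parts it is meant to separate, the scatter rule has no limit, and low scatter would not reveal a stable but mixed reading.

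**The labels agree nominally.** Section 4.5.12 records the iTrace far reading as upwards and the near reading as downwards, so for a lens in its nominal position all devices aim at the same parts. That stands. The difference arises only with rotation, and recording the axis does not show that large rotations are expected.

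**Axis and pupil width are recorded anyway.** Affected eyes can be identified in analysis, and the examination order is implied by section numbering rather than mandated. Both are true, and both soften the point. They still leave mixed readings that cannot be recovered.

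**Small pupils.** A reader might infer that the same fault spoils readings in poorly dilated eyes, and that the Background says full dilation is usually unavailable. The documents do not support this. The Background sentence is conditional, gives no frequency of poor dilation and concerns the Rodenstock device. Small-pupil mixing is also a matter of beam size. An assumed 3 mm zone kept inside a 5 mm pupil can be offset by only 5/2 − 1.5 = 1.0 mm, which puts 11.0% in the wrong part with no rotation at all. Aiming by the marks would leave that unchanged. It is a genuine limitation that the study may properly show.

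**The iTrace's advantage is partly real.** Even aimed vertically, a 1 mm zone at 1.5 mm would not mix until about 70 degrees (arccos(0.5/1.5) = 70.5°). Its tolerance of rotation is thus partly a true property of the device, and only the part of the autorefractor error that re-aiming would remove counts as an artefact.

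**Conclusion.** The point holds in a limited form. The target for far and near readings is defined by vertical halves for the autorefractors and by the lens for the PR50/PR60 and the iTrace. In markedly rotated lenses, autorefractor readings may therefore mix both parts through aiming alone.

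The size cannot be fixed from the protocol. Across assumed zones of 2 to 3 mm at 1.5 mm offset, the wrong-part share is 0 to 2.9% at 30 degrees, 0 to 9.1% at 45 and 7.2 to 19.6% at 60. Within about 20 degrees it is under 1%.

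A reader might go further and conclude that autorefractor readings do mix the parts in rotated eyes generally, or that the comparison is biased toward the iTrace by a known amount. Neither follows: with a zone of 2 or 2.5 mm there is no mixing up to about 34 degrees, and nothing shows how many lenses are rotated beyond that. This is a worthwhile, low-cost improvement to the measurement instructions and does not threaten the study as a whole.

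**What to change.** - Define far part and near part once, by the lens axis, for all mydriatic devices.
- Take the slit-lamp axis reading of 4.5.14 after dilation and before 4.5.10.
- In 4.5.10, replace the upper and lower halves by the direction at right angles to the lens marks, as far as each autorefractor allows.
- Where a device cannot be aimed that way, flag the reading using the recorded axis and mydriatic pupil width, and do not compare it as a pure far or near value.

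**Cost.** No new examination or variable is needed. The slit-lamp examination is reordered or split, and a room change is possible: the slit lamps are in B.6.31, B.6.32 and B.6.35, the autorefractors in B.5.49, B.5.45/46 and B.6.33.1. The eye is exposed to slit-lamp light shortly before the readings. The protocol does not show whether operators can align these automatic devices to the marks, so the flag may be needed often.

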#### 4.5.11 Determination of the focal point in the far and near part of the intraocular lens in Mydriasis using the eye refractometer PR60 or PR50 (Rodenstock, Munich)

(Location: PR50 Cataract center, room B.5.50, Ambulance, room B.6.31+32  
PR60 Ambulance, room B.6.35)

The doctor ensures that the scale of the observer eyepiece is set to 0, or that his own ametropia is correctly taken into account. It is important that the patient's pupils are sufficiently dilated, since the visible annular illumination zone must be placed completely or at least for the most part in the patient's pupil plane. The doctor looks at the test mark images on the retina on the observation beam path and focuses them. The measured value is then read from a scale in diopters. This measuring process is carried out for the far part as well as for the near part of the IOL. For this purpose, the investigator tries to irradiate most of the annular illumination beam path through the far or near part of the IOL.

#### 4.5.12 Determination of the focal point in the far and near part of the intraocular lens in Mydriasis using the iTrace (TraceyTechnologies, Houston, Texas, USA)

(Location: functional diagnostics)

The room lighting is darkened and the window blinds closed. The patient is positioned with the chin on the chin and forehead on the appropriate rests. Afterwards, the patient's head is turned slightly sideways so that the iTrace measuring head can be moved towards the patient's eye. The patient is asked to look through the iTrace and focus on a distant object. It is important to ensure that nothing blocks the patient's gaze, as this affects the patient's accommodation and may result in unwanted refractive readings.

The following measurements are taken in manual mode by selecting the single red wavefront icon in the upper right corner of the screen. The white target is first positioned on the edge of the entrance pupil, outside the center. At the same time, the iTrace is moved back and forth to focus on the iris details and thus set the most suitable measurement plane. The patient is asked to focus on the red light. Pressing the Enter key makes the red scan points visible. For the following measurements the separate 1 mm scan button (64 points) is selected. The scan pattern is centered on the optic center of the implanted multifocal lens. It is important to ensure that the scan pattern is located exactly between the two lens markings of the optics. The patient is asked not to move, to blink twice and then open both eyes wide. The fixation light is switched off with F10. Pressing the button on the joystick triggers the measuring process. If the wavefront measurement points are validly evaluable (visible within the pupil), the measurement is confirmed and saved by selecting the green check mark symbol. Otherwise, the measurement is repeated until a valid evaluation is possible.

Subsequently, a decentered measurement is carried out, 1.5 mm away from the optical center of the multifocal lens in the IOL far and near part, respectively. It is decentered at right angles to the apparent IOL markers and the 1 mm scan pattern is moved from the IOL center 1.5 mm (estimated based on the presented

1 mm grid) into the far or near part of the multifocal lens. In the decentered measurements, care is taken to measure the entire 1mm scan pattern within the pupil and not be affected by iris margins. The measurement in the far part of the multifocal lens is recorded as data point 1.5 mm upwards. The measurement in the near portion of the multifocal lens is recorded as a data point 1.5 mm downwards.

The data collection for the central measurement and the two 1.5 mm decentered measurements are carried out with the WF Verification Display. For this purpose, the respective WF measurement is selected individually without CT measurement in the patient main menu and confirmed with the blue arrow pointing to the right. The refraction value (Sph, Cyl and Axis) is shown in the displayed WF verification window. Furthermore, the SE spot in the RSD (Retinal Spot Diagram) is set as distortion-free as possible by pressing the F1 and F2 keys to determine the focus of the Spherical Equivalent. Care must be taken to ensure that the outermost color ring is used for the evaluation, which guarantees a symmetrical setting (oriented more towards the green ring). The indicated defocus value corresponds to the opposite numerical value of the refraction, plus values must be raised with minus values and minus values must be raised with plus.

#### 4.5.13 Objective determination of the IOL position in the capsular bag based on Sirius Scheimpflug images (Bon-Optik, Lübeck) (Location: Functional diagnostics)

The patient is asked to look straight ahead at the red light spot. The study assistant sees the patient's anterior segment of the eye after starting the program. By moving the joystick back and forth, the operator now adjusts the cornea and pupil center to the displayed areas on the screen. The patient is asked to blink again and then leave the eye wide open. If the patient can not do this alone, the upper lid is stopped with a cotton swab. Pressing the start button on the joystick starts the recording. The Scheimpflug camera now takes 36 pictures, while the camera rotates around the patient's eye. It is important that the patient keeps looking straight ahead until the recording is completed. The program automatically saves this recording for each eye. The employee then finds the most vertical (measurement at 180°) and the most horizontal (measurement at 90°) image out of all recorded images. These study-relevant images are transmitted by the established transfer function in the electronic medical record in FIDUS. In order to calculate the tilt position of the IOL accurately, the stored images are anonymized and forwarded to the company Oculentis.

#### 4.5.14 Slit lamp microscopy in Mydriasis (Location: Ambulance, room B.6.31, B.6.32, B.6.35)

The investigator carries out the ophthalmological examination via a microscope. It is used to observe the eye under high magnification to assess the anterior, middle and posterior structures of the eye and to document any abnormalities or anomalies.

After disinfection of the chin and forehead rest, the patient places his head in the appropriate device. With the aid of various enlargements, the examining doctor has the opportunity to observe the anterior section of the eye in diffuse light first. These include the eyelids, the cornea, the conjunctiva, the anterior chamber, the iris and the pupil. The light is then limited to a slit of about 0.5 mm. This is done by a controller that can individually set the slit size. Now, the front structures are shown by pivoting the slit from different sides in different light incidence angles of the slit light in section.

Subsequently, the assessment of the multifocal intraocular lens is performed. The investigator examines the IOL through the slit for translucency, both in progressive and in regressive light, assesses the anterior capsule and determines

the diameter of the rhexis. Furthermore, it is checked whether the lens sits in the middle of the rhexis or whether it may have come to a decentration. By rotating the slit, the axis position of the multifocal IOL can now be examined. The narrow slit is turned so that it runs parallel to the visible axis of the IOL. Then the investigator can read the axis position on the slit lamp according to the TABO scheme.

For the assessment of the posterior structures of the eye – vitreous, optic nerve and retina or macula – the investigator additionally requires a 90-dpt magnifying glass. The investigator manually places the magnifying glass about 3 cm in front of the patient's eye with progressive light.

Finally, after completion of all examinations, the examiner documents the findings in the data collection sheet as well as the electronic patient file in FIDUS.

## 5. STATISTICAL EVALUATION

The data to be documented are transferred from the electronic patient record and the data collection sheet into an Excel spreadsheet by the study assistants. The patient's name, first name, date of birth, and address are not transferred. The personal data will be replaced by a serial number. Due to this serial number, it can no longer be associated with any particular individual.

The data is then transferred to the program STATISTICA (StatSoft, Inc., Hamburg, Germany) and evaluated.

Main question: Which of the refraction measurement methods allows an accurate and reproducible refraction determination after implantation of a multi-focal intraocular lens LS-313 MF30? The reference method is the determination of the subjective refraction.

